**[Note to interviewer]: For each symptom mentioned ask the following questions:**

Symptom description	
 
• How would you describe this symptom? How does it make you feel?
 
• Tell me about any additional words you use to describe this symptom, if at all.
 

Frequency	
 
• How often do you experience this symptom?
 
• Does the frequency vary/has it changed over time? Please tell me about this.
 
• Does the frequency vary in the daytime versus the nighttime? Tell me about that.
 
• Is it a constant symptom or does it come and go? Tell me about that.
 

Severity	
 
• How would you describe the severity of this symptom?
 
• Does the severity vary/has it changed over time? Please tell me about this?
 
• Does the severity change in the daytime versus the nighttime? Time me about that
 
• How would you describe mild, moderate and severe [insert symptom]?
 

Duration	
 
• How long does this symptom typically last for?
 
• Does the duration vary/has it changed over time? Please tell me about this.
 

Impacts	
 
• How does this symptom affect you in your daily life?
 
• How bothersome is this symptom for you? Please tell me more about that. 
 
○ Physically?
 
○ Doing your daily/usual activities?
 
○ In doing things/relationships with family or friends?
 
○ Emotionally?
 
○ At school/work?
 
 
 

Worsening / Improvement	
 
• Tell me about anything that makes this symptom worse.
 
• Tell me about anything that makes this symptom better.
 

Relation to other symptoms	
 
• Do you experience this symptom on its own or at the same time as other symptoms? Please tell me more about that.
 

**[TO INTERVIEWER]** Please probe on those symptoms in the ‘symptom list’ above, that were not spontaneously mentioned by the participant. Please assess relevance of the symptom first. If the participant experiences the symptom in question please ask the additional questions detailed in the table above.

**8. Have you ever experienced any of the following symptoms as part of your nasal polyps?**

**9. Are there any other symptoms of nasal polyps not already discussed that you have experienced? Please tell me about them.**

**10. Which of the symptoms that you described are the worst? Why?**

**11. Which of the symptoms that you described do you experience most frequently/least frequently?**

**12. Which of the symptoms that you described are most bothersome/least bothersome to you? Why?**

**13. Can you tell me about anything that makes your nasal polyp symptoms better?**

- *Medication?*
- *Coping strategies/lifestyle changes?*

**14. Can you tell me about anything that makes your nasal polyps worse?**

- *Does this affect specific symptoms or do your symptoms worsen equally? Tell me about this.*

- **Living with nasal polyps (10 minutes)**

 *"We are now going to talk about what it is like to live with nasal polyps."*

**15. Tell me what it is like to live with nasal polyps on a daily basis.**

- *How does nasal polyps affect you in your daily life?*
- *Tell me what a good day is like with your nasal polyps. Tell me what a bad day is like with your nasal polyps.*
- *Are there any things that you are not able or find difficult to do because of nasal polyps?*
- *Are there any things that you have to do differently because of nasal polyps? Please tell me about this.*
- *Which symptoms of nasal polyps have had the biggest impact on your life? Tell me why.*

**16. In what ways, if at all, has nasal polyps affected you physically?**

- *How has nasal polyps affected the physical activities you do? Please tell me about this.*
- *Do the physical impacts vary or change over time? (E.g. frequency, severity, duration).*
- *Which symptom(s) of your nasal polyps has the biggest impact on you physically? Why?*
- *Tell me about anything you do to cope with/manage the physical impacts of nasal polyps (e.g. have you made any changes to your life to accommodate these physical impacts?)*

**17. In what ways, if at all, has nasal polyps affected your sleep?**

- *Has nasal polyps affected your sleep quality? Tell me about that.*
- *Has nasal polyps affected how much sleep you can get in in a night? Tell me about that*
- *Which symptom(s) of your nasal polyps has the biggest impact on your sleep? Why?*
- *Tell me what you do to cope with the sleep impacts caused by your nasal polyps.*

**18. In what ways, if at all, has nasal polyps affected you emotionally/psychologically?**

- *Tell me about any emotional impacts you experience as a result of nasal polyps.*
- *Do the emotional impacts vary or change over time? (E.g. frequency, severity, duration).*
- *Which symptom(s) of your nasal polyps has the biggest impact on you emotionally? Why?*
- *Tell me about anything you do to cope with/manage the emotional impacts of nasal polyps*

**19. In what ways, if at all, has nasal polyps affected you in doing things with family and friends?**

- *Has nasal polyps affected your participation in social activities? Tell me about that*
- *Which symptom(s) of your nasal polyps has the biggest impact on your social life? Why?*
- *Has nasal polyps affected your relationships with family/friends? Tell me about that*
- *Which symptom(s) of your nasal polyps has the biggest impact on your relationships with others? Why?*

**20. In what ways, if at all, has nasal polyps affected your work activities?**

- *How do the nasal polyp symptoms that you discussed affect your work activities?*
- *Is there anything that you find challenging at work due to the nasal polyp symptoms that you experience? Please tell me about this.*
- *Have you ever had to take time off work because of your nasal polyps? Please tell me about this.*
- *Which symptom(s) of your nasal polyps has the biggest impact on your work activities? Why?*

**21. In what ways, if at all, has nasal polyps affected you financially?**

- **Treatment/surgical experiences (10 minutes)**

**22. How easy or difficult was it to choose to have surgery? Tell me about the things you considered in making your decision.**

- *When deciding whether to have nasal polyp surgery, which symptom(s) were those you wanted to be reduced the most by surgery?*

**23. Tell me about your experience of having nasal polyp surgery?**

- *What effect did surgery have on your symptoms and any impacts you experienced?*
- *How did having the nasal polyp surgery impact your life?*
- *What were the positives of having surgery (if any)?*
- *Were there any negatives or drawbacks of having surgery?*
- *Would you choose to have additional surgeries to remove your nasal polyps? Why/why not?*

**24. How have the treatments that you have taken for your nasal polyps impacted your life (if at all)? This may include prescribed, over-the-counter and alternative treatments.**

- *What was good about these treatments?*
- *What was bad about these treatments?*

**25. If you were to take a treatment for your nasal polyps, what would make you think that it was worth taking?**

- *How would the symptoms that you experience have to change?*
  - *What change would you like to see in the severity of your symptoms? (probe on the percentage decrease i.e. 50% less or 70% less)*
    - *What is the smallest change that you would be happy with?*
  - *What change would you like to see in how often you experience symptoms?*
    - *What is the smallest change that you would be happy with?*
  - *What change would you like to see in the length of time that your symptoms last for?*
    - *What is the smallest change that you would be happy with?*
  - *What change would you like to see in how bad your symptoms get?*
    - *What is the smallest change that you would be happy with?*
  - *How important is no longer experiencing symptoms at all?*
  - *Which symptoms would be most important to you to treat? Why?*
  - *How would these changes affect your life?*

Date:   /   / 2017  
MM DD

Center Number: /\_\_\_/\_\_\_/

Participant N°: /\_\_\_/\_\_\_/

ADELPHI VALUES

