### **2.2 Secondary**

#### **Combined concept elicitation (CE) and cognitive debriefing (CD) interviews:**

To identify through open-ended questioning the concepts that are important to patients with severe, recurrent, nasal polyps, who have been treated with surgery and the language they use to describe their disease experience. The main areas of exploration will be the symptoms with particular attention paid to the frequency, severity, duration and bother of each symptom, patients' surgical decision-making and surgical/treatment experience and the functional and HRQoL impact experienced by patients.

To cognitively test and explore the content and face validity of existing PRO instruments (single item VAS and SNOT-22) via assessment of the relevance and appropriateness of the items included in the instruments and the participants' ability to read, and consistently understand the instrument item wording, instructions, response option and recall period. The CD interviews will:

- Explore participants' ability to read and consistently understand the item wording, instructions, response options and recall period of the overall and single item VAS and SNOT-22.
- Explore the relevance and appropriateness of all of the items covered by the instruments based on the symptom experience of patients with nasal polyps.
- Verify if the key concepts identified in the concept elicitation phase of the study are adequately assessed by the PRO instruments (confirmation of face validity) and if any gaps exist, provide recommendations for how these could be addressed.
- Explore what level of change in symptoms and/or impacts the patients might consider meaningful. (E.g. what level of change they might consider noticeable and important in response to treatment, and how changes on the item scores might relate to changes in their experience in their symptoms and/or functional impacts.

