### The role of the interviewer is to **inquire** and **support**:

Do not give your own point of view

Be patient and accept silence during open-ended questioning to make sure the patient has time to think about her/his response

Help the patient stick to the topics intended in the guide (but not necessarily in the order presented in the guide)

Help the patient avoid repeating himself or herself

Help the patient cross-reference and make connections that they would not do spontaneously

Ask the patient to clarify any comments that you are not certain you understood and for the benefit of the recording

Ask the patient to explain any vague reference or comment that is pertinent to the research question

**Most importantly:** avoid biasing or leading the patient

**As much as possible your questions should be open-ended and general rather than specific – use suggested probes to follow-up on topics of interest if not adequately discussed in response to the open questions.**

**It is very important that you do not lead the patient with your questions or remarks.** Ask all questions in as open-ended a manner as possible; take care not to bias the patient's response one way or the other. Below for most questions, we have provided a number of possible probes that should help the patient explain his or her thinking when s/he is talking about the topics of interest. These probes are

ADELPHI VALUES

**optional** and do not have to be asked if, when asked the initial question, the patient provides a fully elaborated response and addresses the topics noted in the probes. The probes are only provided for use when the patient finds it difficult to answer your questions, if s/he is reluctant to speak at length about experiences or if key topics of interest have not been elicited spontaneously. You may have to invent your own probes or reword the probes indicated in the interview guide; this is fine. As a fully trained and experienced interviewer we rely on your judgment as to when more information is required from the patient and for you to probe as appropriate.

POSSIBLE NON-LEADING PROBES MIGHT INCLUDE:

- Can you describe exactly how that feels?
- Tell me more about that.
- How does that affect you?
- Can you talk more about \_\_\_\_\_?
- How often does that happen?
- How long does that last?
- Is there anything that makes it better or worse?

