During the interview, it is not essential for you to ask the questions in exactly the way that they are written in this guide and for some interviewees it may be necessary for you to reword questions as a means to enable open-discussion. If you reword a question; however, you should be sure to avoid biasing the patient’s response. If a topic has been covered sufficiently in an earlier part of the discussion it is not necessary to go over it again later if this topic comes up later in the interview guide.

If the patient directs any questions to you that are of a medical nature, please explain that you are not a medical professional and that the patient should direct any medical queries to his or her doctor or nurse.

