**Using the interview guide**

Throughout this guide we have coded the questions and instructions so that it is clear which questions are required and which are probes and do not necessarily need to be asked. The code is as follows:

Blue font	These are instructions to you
	These are statements that you are to read aloud word-for-word
1.	Questions prefixed by a specific number must be posed to all patients
•	All probes are bulleted – these do not need to be used specifically but are included to assist you in drawing further information from the patients

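### The optional severity probe in question 25 of the interview guide supplies two large percentage reductions, against the guide's own rule not to lead the patient (minor)

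*Combined protocol and SAP*

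**What the plan says.** Question 25 in Appendix 7 is the numbered question on what would make a treatment worth taking. Beneath it are bulleted probes on how symptoms would have to change, with four parallel sub-probes: severity, frequency, duration, and how bad the symptoms get. The severity sub-probe comes first and carries a parenthesis telling the interviewer to "probe on the percentage decrease i.e. 50% less or 70% less". The next line asks "What is the smallest change that you would be happy with", and the same follow-up is attached to each of the other three sub-probes.

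The guide's section on the role of the interviewer states "It is very important that you do not lead the patient with your questions or remarks" and continues "Ask all questions in as open-ended a manner as possible; take care not to bias". The warning returns where rewording is permitted: "If you reword a question; however, you should be sure to avoid biasing".

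Bulleted probes are optional. The key to using the guide says that "these do not need to be used specifically but are included to assist you in drawing further information from the patients". The role section narrows their use: "The probes are only provided for use when the patient finds it difficult to answer your questions". It adds two further triggers: reluctance to talk at length, and a key topic that has not come up unprompted.

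Meaningful change is a stated area of inquiry. Section 2.2 lists, among the aims of the cognitive debriefing, "Explore what level of change in symptoms and/or impacts the patients might consider meaningful".

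**The concern.** The patient is meant to define how much change is enough. A prompt that names candidate values can shape the answer, and this one names only 50% and 70%. A patient who would have settled for less hears nothing near that answer before being asked for the smallest acceptable change. The prompt is also most likely to reach patients who have not produced a figure themselves.

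At stake is how credible the percentages reported from question 25 are as patients' own views. The study is meant to inform the sponsor's clinical outcome assessment strategy (Section 1), and the VAS items debriefed are those proposed for the Phase III trial (Appendix 7, interview objectives).

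**Working it through.** The plan gives no figure to reproduce here and no calculation applies. The check sets the relevant parts of the guide side by side.

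1. **Form of the probe.** The parenthesis is introduced by *i.e.*, which read literally defines the probe by the two values. Neither is below 50%. Nothing marks them as background for the interviewer only.

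2. **Against the rule.** The role section bars leading and asks for openness. It lists seven sample non-leading probes, none of which supplies a value. Naming two possible answers to a quantity the patient is asked to define does not meet that standard.

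3. **Whether the figures are needed.** Of the four parallel sub-probes, one (severity) carries figures and three do not. The guide therefore asks the same kind of question three times without examples.

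4. **Order.** Within question 25, the open numbered question, the general probe on how symptoms would have to change, and the severity question itself all come before the parenthesis. A patient can therefore answer unprompted first. The parenthesis comes before all four smallest-change follow-ups and immediately before the first of them.

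5. **Who may hear the figures.** Planned interviews are 20 in the US plus 10 in Germany, 30 in all. Only numbered questions must be put to everyone, so the number exposed lies between 0 and 30 and cannot be narrowed from the documents. The conditions for using probes make exposure more likely among patients who struggle to answer.

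6. **What else bears on meaningful change.** The SNOT-22 and VAS debriefing tables ask, item by item, what shift in score would matter to the patient and why. None of these questions contains an example value.

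7. **Whether prompted answers can be recognised.** Sections 3.3 and 4 provide for recording and full transcription of every interview, so a figure spoken by the interviewer would appear in the transcript. However, the plan does not ask anyone to look for it. The symptom list in the guide has a column for spontaneous mention; question 25 has no equivalent, and Section 4 does not separate prompted from volunteered percentages.

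8. **Size of any pull.** The documents contain no data on anchoring, so no estimate is possible.

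**The case against.** The best reply is that the parenthesis is a note to a trained interviewer, not a script. The guide has a separate code for statements to be read out word for word, and this text is not presented as one. Probes are optional and may be reworded if bias is avoided. Read this way, the two figures only show the kind of answer wanted, a percentage. Open questions come first, only one sub-probe is affected, and the sub-probe on how bad symptoms get covers similar ground without figures.

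The documents also place the meaningful-change aim in the cognitive debriefing (Sections 2.2 and 3.3, and the aims in Appendix 7), whereas question 25 belongs to concept elicitation. There are no endpoints (Section 3.3.1), and Section 4 rules out quantitative analysis of the interview data beyond possibly reporting how many participants mention an issue.

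Most of this stands, and it is why the point is minor. It does not remove the conflict. Even as an instruction to the interviewer, the text says to probe on two named values, and nothing says to withhold them. Optional status does not protect the patients most likely to be probed. If the figures are meant only to show a format, the guide should say so.

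**Conclusion.** The conflict between the severity sub-probe and the no-leading rule is real, and its severity is minor. Where the probe is used and the figures are spoken, answers may be pulled towards 50% and 70%. This rests on two assumptions: that some interviewers will voice the figures, and that supplied values can influence answers. Neither frequency nor effect size can be obtained from the documents.

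A reader might infer more than the documents support:

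- *That all 30 patients are anchored.* All interviews use the guide, but this text sits inside an optional probe.
- *That answers will cluster at the figures and cannot be separated from patients' own views.* Clustering is a possibility without supporting data, and the transcripts will show who first named a figure.
- *That only very large VAS changes would count.* With overall VAS entry above 70 on a 0 to 100 scale, one could compute 0.5 × 70 = 35 to 0.5 × 100 = 50 points, and 0.7 × 70 = 49 to 0.7 × 100 = 70 points. Question 25 does not mention the VAS, nothing in the plan makes this conversion, and the next line asks for the smallest acceptable change.
- *That the debriefing answers are compromised.* Those questions come later, so carry-over is conceivable. They are open, free of figures and framed in scores, and nothing in the documents shows carry-over.
- *That a Phase III threshold would be biased.* The plan does not say that any responder threshold will be derived from question 25.

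**What to change.** Delete the two percentages and the abbreviation introducing them, and ask for a figure openly, for example: *How much less would it need to be? Can you put a number on that?*

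If the figures are kept to show the answer format, mark them as not to be read aloud. Also add a line to the coding scheme in Section 4 so that each percentage is coded as volunteered or prompted; the transcripts already supply the information.

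Moving the smallest-change question ahead of the desired-change question is a matter of preference and is not needed to resolve the conflict.

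The cost is a one-line update to the guide and any translation used for the German interviews, plus notification to the ethics boards if they require it. Interview length and sample size are unaffected.

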**26. Is there anything else you would like to tell me about your nasal polyps that we haven't already discussed?**

## 27. Think aloud cognitive debriefing (60 minutes)

---

**[TO INTERVIEWER]** Ask the participant to read **aloud** the instructions, each item and the responses they choose for each questionnaire. After the participant has responded to each item ask the participant the corresponding questions in the table below. Ask the participant to complete **all** of the questions.

- 💡 *“For each instruction and question of each of the following questionnaires, I want you to read it out loud, and tell me what you are thinking when you are answering. Please tell me any thoughts or opinions you have on the instructions and questions as you read them and tell me why you selected the answer you did.”*
- 💡 *“After you respond to each question I am going to ask you some questions about each instruction/item. These will be about your understanding of the item and its relevance to your experience with nasal polyps. Additionally, I will ask you about the response options you selected for each assessment and what it would mean to you to select a different response option.”*
- 💡 *“You may decline to answer any question”*
- 💡 *“The questions I ask may be a bit repetitive, but they are important so that we can see how you understand each question.”*

**[TO INTERVIEWER]**

## Interviewer instructions

- You may need to keep reminding the participant to read and think aloud. Please have the patient read aloud the response they have chosen so this can be recorded.
- If the participant has difficulty reading a particular item, offer to read it for them and make a note of this.
- **Make sure you are non-judgmental in your tone** when probing. If the participant hesitates when answering, use one or more of the following probes, or similar questions to elicit comments from them. Please feel free to vary which ones you ask for each questionnaire item – rather than going through each one in rote fashion and getting one word answers. **Not every probe has to be used for every item/participant.**
- **Asking why:** if appropriate, probe further by asking the participant why they have answered the interview question in that way.
- If the patient has chosen to **skip a question** remember to ask why they have chosen to do so.
- If the patient has chosen “0” or “not applicable” option for any question ask why they have made this selection
  - Was the question not relevant? (e.g. they do not experience this symptom)
  - Is the question relevant, although they might not be currently experiencing this symptom?
- Wherever possible, please make brief notes in the empty boxes provided for each item to summarize:
  - How the question was **understood** by the participant?
  - Was the concept **relevant** to the participant?
  - How **easy/difficult** was it for the participant to choose their answer?
  - Why did they choose the answer they did? [please record their answers in the box below]

Date:  /  / 2017  
MM DD

Center Number: /\_\_\_/\_\_\_/

Participant N°: /\_\_\_/\_\_\_/

• **Cognitive debriefing of the SNOT-22**

ADELPHI VALUES

Understanding	Relevance	Recall period	Response Options

[INSTRUCTION 1] Below you will find a list of symptoms and social/emotional consequences of your rhinosinusitis. We would like to know more about these problems and would appreciate your answering the following questions to the best of your ability. There are no right or wrong answers and only you can provide us with this information. Please rate your problems as they have been over the past two weeks. Thank you for your participation. Please do not hesitate to ask for assistance if necessary.
			

In your own words, what is this instruction asking you to do? What does “social/emotional consequences” mean to you? What does “rhinosinusitis” mean to you? What does “problems” in relation to your condition mean to you?
		
What does “over the past two weeks mean to you”? How easy or difficult is it to remember your symptoms over the last two weeks? Do you think that it is appropriate to answer questions about your nasal polyps thinking back to the past two weeks? Tell me about that.
	

[INSTRUCTION 2] Considering how severe the problem is when you experience it and how often it happens, please rate each item below on how “bad” it is by selecting the number that corresponds with how you feeling using this scale.
			

In your own words, what is this instruction asking you to do? What does “severe” mean to you? What does “how bad” mean to you? What does “how often it happens” mean to you? What does “corresponds with how you are feeling” mean to you?
	
Based on your experience of nasal polyps, do you think that how bad your symptoms are (severity) and how often you experience a symptom (frequency) can be assessed at the same time? Are they the same or different? Why?
		
How would you describe: “No problem” “Very Mild Problem” “Mild or Slight Problem” “Moderate Problem” “Severe Problem” “Problem as bad as it can be”

[QUESTION 1] Need to blow nose
			

What does “need to blow nose” mean to you? Would you use any other words to describe this symptom?
	
Do you experience this as part of your nasal polyps? Why did you choose an answer of [X]? Would your score be different if you were asked to rate the severity and frequency of your “need to blow nose” separately, rather than together? Why?
	
What time frame were you thinking about when answering this question? Was it easy or difficult to remember over the past 2 weeks? Did you think about both how bad the symptom is and how often you experience it? Why/Why not?
	
How easy or difficult was it for you answer this question? Why? What change in score would make a difference to you and why?

ADELPHI VALUES

Understanding	Relevance	Recall period	Response Options
	What would your severity based and frequency based scores be?		
[QUESTION 2] Nasal blockage			

What does “nasal blockage” mean to you?
 
Would you use any other words to describe this term?
 
Is “nasal blockage” the same or different to “need to blow nose”? Why?
	
Do you experience this as part of your nasal polyps?
 
Why did you choose an answer of [X]?
 
Would your score be different if you were asked to rate the severity and frequency of your “nasal blockage” separately, rather than together? Why?
 
What would your severity based and frequency based scores be?
		
How easy or difficult was it for you answer this question? Why?
 
What change in score would make a difference to you and why?

[QUESTION 3] Sneezing			

What does “sneezing” mean to you?
 
Would you use any other words to describe this term?
	
Do you experience this as part of your nasal polyps?
 
Why did you choose an answer of [X]?
 
Would your score be different if you were asked to rate the severity and frequency of your “sneezing” separately, rather than together? Why?
 
What would your severity based and frequency based scores be?
		
How easy or difficult was it for you answer this question?
 
What change in score would make a difference to you and why?

[QUESTION 4]: Runny nose			

What does “runny nose” mean to you?
 
Would you use any other words to describe this term?
 
Is “runny nose” the same or different to “a need to blow nose”? Why?
 
Is “runny nose” the same or different to “nasal blockage”? Why?
	
Do you experience this as part of your nasal polyps?
 
Why did you choose an answer of [X]?
 
Would your score be different if you were asked to rate the severity and frequency of your “runny nose” separately, rather than together? Why?
		
How easy or difficult was it for you answer this question? Why?
 
What change in score would make a difference to you and why?

ADELPHI VALUES

Understanding	Relevance	Recall period	Response Options
	What would your severity based and frequency based scores be		
[QUESTION 5] Cough			

What does “cough” mean to you? Would you use any other words to describe this term?
	
Do you experience this as part of your nasal polyps? Why did you choose an answer of [X]? Would your score be different if you were asked to rate the severity and frequency of your “cough” separately, rather than together? Why? What would your severity based and frequency based scores be?
	
What time frame were you thinking about when answering this question? Was it easy or difficult to remember over the past 2 weeks? Did you think about how bad the symptom is and how often you experience it? Why/Why not?
	
How easy or difficult was it for you answer this question? Why? What change in score would make a difference to you and why?

[QUESTION 6] Post-nasal discharge			

What does “post-nasal discharge” mean to you? Would you use any other words to describe this term? Is “post-nasal discharge” the same or different to “runny nose”? Why?
	
Do you experience this as part of your nasal polyps? Why did you choose an answer of [X]? Would your score be different if you were asked to rate the severity and frequency of your “post-nasal discharge” separately, rather than together? Why? What would your severity based and frequency based scores be?
		
How easy or difficult was it for you answer this question? Why? What change in score would make a difference to you and why?

[QUESTION 7] Thick nasal discharge			

What does “thick nasal discharge” mean to you? Would you use any other words to describe this term? Is “thick nasal discharge” the same or different to “runny nose”? Why? Is “thick nasal discharge” the same or different to “post-nasal
	
Do you experience this as part of your nasal polyps? Why did you choose an answer of [X]? Would your score be different if you were asked to rate the severity and frequency of your “thick nasal discharge” separately, rather than together? Why?
		
How easy or difficult was it for you answer this question? Why? What change in score would make a difference to you and why?

ADELPHI VALUES

Understanding	Relevance	Recall period	Response Options
discharge"? Why?	What would your severity based and frequency based scores be?		
[QUESTION 8] Ear fullness			

What does "ear fullness" mean to you? Would you use any other words to describe this term?
	
Do you experience this as part of your nasal polyps? Why did you choose an answer of [X]? Would your score be different if you were asked to rate the severity and frequency of your "ear fullness" separately, rather than together? Why? What would your severity based and frequency based scores be?
		
How easy or difficult was it for you answer this question? Why? What change in score would make a difference to you and why?

[QUESTION 9] Dizziness			

What does "dizziness" mean to you? Would you use any other words to describe this term?
	
Do you experience this as part of your nasal polyps? Why did you choose an answer of [X]? Would your score be different if you were asked to rate the severity and frequency of your "dizziness" separately, rather than together? Why? What would your severity based and frequency based scores be?
		
How easy or difficult was it for you answer this question? Why? What change in score would make a difference to you and why?

[QUESTION 10] Ear pain			

What does "ear pain" mean to you? Would you use any other words to describe this term? Is "ear pain" the same or different to "ear fullness"? Why?
	
Do you experience this as part of your nasal polyps? Why did you choose an answer of [X]? Would your score be different if you were asked to rate the severity and frequency of your "ear pain"
	
What time frame were you thinking about when answering this question? Was it easy or difficult to remember over the past 2 weeks? Did you think about how bad the
	
How easy or difficult was it for you answer this question? Why? What change in score would make a difference to you and why?

ADELPHI VALUES

Understanding	Relevance	Recall period	Response Options
	separately, rather than together? Why? What would your severity based and frequency based scores be?	symptom is and how often you experience it? Why/Why not?	
[QUESTION 11] Facial pain/pressure			
What does “facial pain” mean to you? What does “facial pressure” mean to you? Is “facial pain” the same or different to “facial pressure”? Why? Would you use any other words to describe these terms? Where on the face do you think about? Full face or specific areas? Tell me about that.	Do you experience this as part of your nasal polyps? Why did you choose an answer of [X]? Do you think that it’s appropriate to assess facial pain and pressure in one question? Why/why not? Would your scores be different if you were asked to rate “facial pain” and “facial pressure” separately? Would your score be different if you were asked to rate the severity and frequency of your “facial pain” and “facial pressure” separately, rather than together? Why? What would your severity based and frequency based scores be for each?		How easy or difficult was it for you answer this question? Why? What change in score would make a difference to you and why?
[QUESTION 12] Decreased sense of smell/taste			
What does a “decreased sense of smell” mean to you? What does a “decreased sense of taste” mean to you? Would you use any other words to describe these terms?	Do you experience this as part of your nasal polyps? Why did you choose an answer of [X]? Do you think that it’s appropriate to assess decreased sense of smell and taste in one question? Why/why not? Would your scores be different if you were asked to rate “decreased smell” and “decreased taste” separately?		How easy or difficult was it for you answer this question? Why? What change in score would make a difference to you and why?

ADELPHI VALUES

Understanding	Relevance	Recall period	Response Options
	
Would your score be different if you were asked to rate the severity and frequency of your “decreased sense of smell” and “decreased sense of taste” separately, rather than together? Why?
 
What would your severity based and frequency based scores be for each?
		

[QUESTION 13] Difficulty falling asleep
			

What does difficult falling asleep mean to you?
	
Do you experience this as part of your nasal polyps? Why did you choose an answer of [X]? Would your score be different if you were asked to rate the severity and frequency of your “difficulty falling asleep” separately, rather than together? Why? What would your severity based and frequency based scores be?
	
What time frame were you thinking about when answering this question? Was it easy or difficult to remember over the past 2 weeks? Did you think about how bad the impact is and how often you experience it? Why/Why not?
	
How easy or difficult was it for you answer this question? Why? What change in score would make a difference to you and why?

[QUESTION 14] Wake up at night
			

What does waking up at night mean to you?
	
Do you experience this as part of your nasal polyps? Why did you choose an answer of [X]? Would your score be different if you were asked to rate the severity and frequency of your “waking up at night” separately, rather than together? Why? What would your severity based and frequency based scores be?
		
How easy or difficult was it for you answer this question? Why? What change in score would make a difference to you and why?

ADELPHI VALUES

Understanding	Relevance	Recall period	Response Options
[QUESTION 15] Lack of a good night's sleep			

What does "lack of good night's sleep" mean to you?
 
Is "lack of good night's sleep" and "waking up at night" the same or different? Why?
 
Is "lack of a good night's sleep" and "difficulty falling asleep" the same or different? Why?
	
Do you experience this as part of your nasal polyps?
 
Why did you choose an answer of [X]?
 
Would your score be different if you were asked to rate the severity and frequency of your "lack of good night's sleep" separately, rather than together? Why?
 
What would your severity based and frequency based scores be?
		
How easy or difficult was it for you answer this question? Why?
 
What change in score would make a difference to you and why?

[QUESTION 16] Wake up tired			
